8. During Session 8, the interventionist will schedule the following appointments, contacting the patient one day before all subsequent tasks to remind them:
 - a. Post-intervention appointment at the VA to complete assessment and return equipment (1 week later)
 - b. Booster session (to be completed via phone 5 weeks later)
 - c. Questionnaire #3, to be completed 9 weeks later
 - d. Questionnaire #4, to be completed 17 weeks later
9. The final session at the VA (Week 8) will include the following tasks:

- a. Returning of mobile phones (if applicable) and breathalyzers
- b. Post-intervention assessment battery, completed using a laptop
- c. Reminder of all subsequent appointments/tasks for the study
10. At 12 weeks, the interventionist will contact the participants to complete a 30-minute intervention booster session via phone. This session will review the participant's drinking goals and provide a refresher on the different types of triggers and strategies to address them.
11. At 16 weeks, the interventionist will contact the participants and ask them to complete a follow-up assessment battery at home (on a computer, tablet, or mobile phone—no clinic visit will be required)
 - a. Participants will be given the option to come to the VA to complete the questionnaire if desired
 - b. If assessment is not done within a week, researchers will contact the participant to encourage participation and ensure that no adverse events had occurred
 - i. If patients cannot be reached, researchers will attempt to contact them three additional times (one day later, three days later, and one week later). If they cannot be contacted by the third attempt, they will be considered lost to follow-up and will not be contacted again.
12. At 24 weeks, the interventionist will contact the participants and ask them to complete an additional follow-up assessment battery at home (on a computer, tablet, or mobile phone)—no clinic visit will be required
 - a. Participants will be given the option to come to the VA to complete the questionnaire if desired
 - b. If assessment is not done within a week, researchers will contact the participant to encourage participation and ensure that no adverse events had occurred

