- After Session 5: \$20 for phone session, up to \$15 for daily monitoring
- After Session 6: \$20 for phone session, up to \$15 for daily monitoring
- After Session 7: \$20 for phone session, up to \$15 for daily monitoring
- After Session 8: \$20 for phone session, plus up to \$15 for daily monitoring

- After Week 16 visit to the VA: \$40 for questionnaire, plus up to \$15 for daily monitoring
- After Week 20 Booster Session: \$20
- After Week 24 questionnaire: \$40

Study Schedule

Participants in the waitlist-controlled trial will be enrolled in the study for a total of 24 weeks (168 days), whether they are in the intervention or waitlist-control group. They will participate in eight intervention sessions and one booster session. The first and last sessions will take 1.5-2 hours, depending on how long the participants take to complete the surveys. Sessions 2-8 and the booster session will take 30 minutes each. After each intervention session, they will complete a short 5-minute questionnaire on their mobile phones. During the intervention, they will also complete two daily assessments, which will take approximately 20 minutes total. Each participant will also complete two additional assessment batteries, which will take 45-60 minutes. Thus, the total time commitment is approximately 27-28 hours. On the rare occasion when study visits may be unexpectedly delayed, visits will not be delayed more than 1 week. See the following flowchart for detailed information about the participant timeline.

Patient Compensation

Participants will receive the following:

- \$20 for attending all intervention sessions via videoconferencing or phone (including booster session – 9 sessions)
- \$1 for each completed breathalyzer reading (up to 14/week, with \$1 bonus for completing all readings)
- \$30, \$40, \$40, and \$40 for completing health questionnaires
- TOTAL POSSIBLE: \$450

5. Data

Collection and record keeping

Both intervention and waitlist-control groups will complete an extensive assessment battery at baseline, 8 weeks, 16 weeks, and 24 weeks. They will also complete daily monitoring of alcohol and medication use during their 8-week intervention period. The following outcome variables will be explored via the listed methods of data collection:

Confidential online questionnaires, completed on tablets or mobile phones at baseline, and 8-, 16-, and 24 week follow-ups, concerning the following variables:

- Post-Traumatic Stress Disorder Symptoms

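### In the intervention group, the week-16 loss-to-follow-up rule rules out the week-24 contact that the protocol plans for every participant

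*Combined protocol and SAP*

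**What the plan says.** Section 4 (Study Design), Step 3a, item 11 covers the week-16 follow-up in the intervention group. Item 11b begins: "If assessment is not done within a week, researchers will contact the participant to encourage participation and ensure that no adverse events had occurred". If that contact fails, "researchers will attempt to contact them three additional times (one day later, three days later, and one week later"). Item 11b(i) then closes: "If they cannot be contacted by the third attempt, they will be considered lost to follow-up and will not be contacted again".

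Other passages assume that contact continues:

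- Item 8 of Step 3a has appointments booked during Session 8, with staff "contacting the patient one day before all subsequent tasks to remind them". Item 8d lists among them "Questionnaire #4, to be completed 17 weeks later".
- Item 12 opens: "At 24 weeks, the interventionist will contact the participants and ask them to complete an additional follow-up assessment battery at home". It makes no exception for people lost at week 16.
- Study Schedule: "Participants in the waitlist-controlled trial will be enrolled in the study for a total of 24 weeks (168 days"), in either group.
- The account of data collection in section 5 states: "Both intervention and waitlist-control groups will complete an extensive assessment battery at baseline, 8 weeks, 16 weeks, and 24 weeks".

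The same loss-to-follow-up sentence appears twice more, in Step 3a item 12b(i) and Step 3b item 15b(i). Both concern week 24, after which no assessment remains.

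**The concern.** Someone who does not answer around week 16 has not withdrawn, yet item 11b(i) treats them as if they had. The week-24 battery starts with a study contact, so a ban on contact means it is never requested.

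The protocol itself gives reason to expect temporary gaps. Step 2 item 6 requires a study phone for people whose service was cut off for cost within the past year. Step 3a item 9a has study phones returned at week 8. By week 16 those people depend on their own service again.

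Three things are at stake:

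- **Planned data.** Week 24 in the intervention group is the trial's only questionnaire more than two months after the intervention ends.
- **Retention.** Section 3 makes feasibility an objective and names recruitment, engagement and adherence. Retention bears on engagement, and this rule creates some attrition of its own.
- **Safety contact.** In Step 3a, only items 11b and 12b provide explicitly for an adverse-event check. A person never reached under the first cannot receive the second.

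**Working it through.** **1. The plan's own calendar.** 24 weeks × 7 = 168 days, as stated. The post-intervention visit at week 8 is one week after Session 8, so Session 8 falls at week 7. The other bookings agree: 7 + 5 = 12 (booster), 7 + 9 = 16 (Questionnaire #3), 7 + 17 = 24 (Questionnaire #4). The week-24 assessment is therefore a deliberate part of the schedule.

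**2. When contact ends under item 11b(i).**

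- Week-16 request: 16 × 7 = day 112.
- Contact after a week without completion: 112 + 7 = day 119.
- Last further attempt, if all three intervals run from that failed contact: 119 + 7 = day 126, or week 18.0.
- Last further attempt, if the intervals are cumulative: 119 + (1 + 3 + 7) = day 130, or week 18.6.

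The rule thus needs four failed contacts (one plus three) and takes effect 14 to 18 days after the week-16 request. From there to the week-24 request (day 168) is 42 or 38 days, that is 6.0 or 5.4 weeks. Like for like, the conditional adverse-event contact falls at about week 17 for the week-16 battery and about week 25 for the week-24 battery, 8 weeks apart.

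**3. Which group is affected.**

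| | Intervention | Waitlist |
|---|---|---|
| Week 16 | Remote questionnaire, with the rule | Clinic visit, no such rule |
| Week 24 | Remote questionnaire, with the rule | Remote questionnaire, with the rule |
| Assessment still to come when the rule first applies | Week 24 | None |
| Week 24, measured from the end of the intervention | 24 − 8 = 16 weeks | 24 − 16 = 8 weeks |

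**4. Which analyses use the intervention group's week 24.** The SAP compares the groups at the end of the first 8 weeks. Its long-term model pools both groups and names two time points after the start of treatment: T2 and T3 for the intervention group (weeks 8 and 16), T3 and T4 for the waitlist group. Intervention T4 (week 24) is in no named model. It is covered by the SAP's general undertaking to summarise outcome variables descriptively.

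**5. Illustration of size.** The documents give neither an allocation ratio nor an unreachable rate. Assume 25 of the 50 are in the intervention group and 5% to 25% are unreachable at week 16.

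- Never asked for week 24: 25 × 0.05 = 1.25 to 25 × 0.25 = 6.25, so about 1 to 6 people.
- Chance that at least one person is affected: 1 − 0.95^25 = 72% at a 5% rate, and above 99% at 20%.
- If half of them could have been reached at week 24 (also an assumption), the loss due to the rule itself is 0.6 to 3.1 people.

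**The case against.** A cap on contact attempts is a legitimate operational choice, and this one is not hasty: a reminder, a request, a week's grace and four failed contacts come first. Questionnaire #4 is booked with the participant in Session 8 and mentioned again at week 8, and nothing stops the participant from getting in touch. Viral load comes from chart review and needs no contact, although that review is worded as following study completion. Section 3 describes a two-month follow-up, which for the intervention group is week 16, and item 12 presents week 24 as an extra assessment. All of this stands, and it makes the point a small one.

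A reader might infer four stronger things that the documents do not support:

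- **That missing week-24 data in one group bias the results.** No named between-group comparison or model uses the intervention group's week 24.
- **That data are thrown away.** Nothing collected is discarded; the week-24 data are simply not requested.
- **That a scheduled safety check is cancelled.** The week-24 adverse-event contact happens only if the questionnaire is a week late, and participants who answer on time never receive it. An emergency contact is also held, for emergencies only.
- **That those lost are heavier or relapsed drinkers.** This is plausible, but nothing in the documents shows it.

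The objection does not remove the conflict: item 11b(i) forbids a contact that items 8 and 12 require.

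**Conclusion.** The conflict is real and rests on the text alone. For an intervention participant not reached at week 16, item 11b(i) cannot be followed together with items 8d and 12 and the 24-week assessment schedule in section 5. Only the intervention group can lose a later assessment this way.

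The consequence is minor. It concerns descriptive week-24 data, the retention figure and a conditional adverse-event contact; the 8-week comparison and the long-term model are untouched. The estimate of about 1 to 6 people never asked depends on the assumed group size and unreachable rate. The number actually lost because of the rule is smaller, since some would not have responded at week 24 anyway. This is a low-cost improvement and does not threaten the trial's conclusions.

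**What to change.** Reconcile the passages by limiting item 11b(i) to the assessment it concerns. After the failed attempts, record the week-16 assessment as missing. Keep the week-24 reminder and request, with the same contact attempts, for everyone who has not withdrawn consent. Declare loss to follow-up only after the week-24 attempts fail. Step 3a item 12b(i) and Step 3b item 15b(i) can stay as they are.

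The cost is one changed sentence and a few calls by existing staff. Per person this is at most one reminder, one request, one contact after a week and three further attempts: 1 + 1 + 1 + 3 = 6. For 1 to 6 people that is 6 to 36 contacts over the whole trial.

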 - c. Have you ever had to cancel or shut off your cell phone service for a period of time because the cost of maintaining the service was too expensive? (Y/N)
 - i. If yes, how recently did this occur? (More than a year ago/Less than a year ago)
 1. If less than a year, inform participant that they must use a study phone, which will be provided at their first appointment
 - d. Do poor or dropped signals prevent you from using your cell phone? (Y/N)
 - i. If yes, inform the participant that they may need to use a study phone. The interventionist will contact them before their first appointment to determine if one is needed.
 - e. How often do you reach the maximum amount of data you are allowed to use as part of your cell phone plan? (Frequently/Occasionally/Rarely/Never)
 - i. If "frequently" or "occasionally," inform the participant that they must use a study phone, which will be provided at their first appointment.
 - f. If responses indicate that they can use their own phone: Ask the participant to view the instructions for downloading the BACTrack app in the Participant Manual and ask them to download it to their phone before coming in for the initial meeting.
7. After the research coordinator asks these questions they will also ask the participant to provide information on their best emergency contact. The participant will be notified that this emergency

contact will only be called if necessary and that all information regarding their involvement in the study will be kept confidential.

- a. If it is an emergency and a patient cannot be reached, study staff will reach out to the emergency contact
8. The research coordinator will then notify the study interventionist through email of the newly-recruited patient by providing the Study ID number only.
9. The interventionist will be notified of a patient's initial appointment time through the shared calendar.
10. One day before the videoconferencing session, the interventionist will contact the participant to remind them of their appointment.

Step 3: Intervention Delivery

3a. Intervention group

1. One day before the videoconferencing session, the interventionist will contact the participant to remind them of their appointment.
 - a. If they are using their own phone and were not able to download the app before the last contact point, check in regarding the app installation at this point

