 - i. If patients cannot be reached, researchers will attempt to contact them three additional times (one day later, three days later, and one week later). If they cannot be contacted by the third attempt, they will be considered lost to follow-up and will not be contacted again.
13. After the participant completes the study, a retrospective chart review will be conducted to obtain viral load measurements (minimum of 2) from the participant during the time period beginning 3 months prior to their entry into the study and up to 6 months after their entry into the study.

3b. Waitlist-control group

1. After randomization and enrollment, the participant will complete the baseline assessment either at the time of enrollment, at home, or during a subsequent appointment within the next 30 days
2. The interventionist will call the participant after enrollment and do the following:
 - a. Introduce themselves to the patient
 - b. Describe the study timeline
 - c. Discuss follow-up contact times and encourage the participant to stay in contact
 - d. Remind participant of incentives they will receive for participating
 - e. Provide information about the baseline assessment (if the participant has not already completed it)
3. The interventionist will contact participants using their chosen method of communication after 4 weeks to maintain contact and ensure that no adverse events have occurred
4. At 7 weeks, the interventionist will contact participants to obtain their availability for the next week to schedule the first intervention content session based on the shared calendar
5. One day before the videoconferencing session, the researcher will contact the participant via the participant's chosen method of contact to remind them of their appointment
6. At 8 weeks, the patient will come into the clinic to begin the intervention.
7. The patient will be given a laptop to complete the initial assessment battery
8. If the participant is in need of a study phone, the VA coordinator will provide this phone, along with the breathalyzer, to the participant
9. The participant will begin the first intervention session, which will consist of the following content/tasks:
 - a. Introductions and orientation to the technology (smartphone and breathalyzer, stored at the clinic; tutorial handouts provided)

- b. Review of self-monitoring procedures and setting of “do not disturb” hours
 - c. Review of breathing awareness exercise

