 - d. Scheduling follow-up intervention sessions for sessions 2-8, conducted via mobile phone.
 - e. A short post-session satisfaction survey, delivered via text message and completed immediately following the session.
10. The day after the first session, participants will begin self-monitoring their alcohol, medication use, and mental health
- a. They will be texted at two random times each day using an automated software to complete a breathalyzer reading and finish a survey
 - b. If participants do not respond to the request within 30 minutes by replying with “C” to confirm they completed the tasks, a text reminder will be sent, followed by another an hour later.
 - i. If the participant is in a situation where they are unable to complete the breathalyzer test, they will be able to respond to the text message and request a follow-up reminder two hours later.
 - c. If participants wish to go to sleep for the night and have not yet received their evening reminder, they can elect to complete a breathalyzer reading and survey before going to bed.
 - d. Self-monitoring will continue until the day of the final intervention session
 - e. Participants will be instructed to call the interventionist if they have any technical difficulties throughout the course of the study
11. Sessions 2-8 of the intervention will be conducted via phone call, with patients instructed to find a private room from which to speak with their counselor
- a. After each session, participants will complete a short post-session satisfaction survey, delivered via text message and completed immediately following the session
12. During Session 8, the interventionist will schedule the following appointments, contacting the patient one day before all subsequent tasks to remind them:
- a. Post-intervention appointment at the VA to complete assessment and return equipment (1 week later)
 - b. Booster session (to be completed via phone 5 weeks later)
 - c. Questionnaire #4, to be completed 9 weeks later
13. The final session at the VA (Week 16) will include the following content/tasks:
- a. Returning of mobile phones and breathalyzers
 - b. Post-intervention assessment battery, completed using a laptop
 - c. Reminder of all subsequent appointments/tasks for the study

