14. At 20 weeks, the interventionist will contact the participants to complete a 30-minute intervention booster session via phone. This session will review the participant’s drinking goals and provide a refresher on the different types of triggers and strategies to address them.
15. At 24 weeks, researchers will contact the participants and ask them to complete a follow-up assessment battery at home (on a computer, tablet, or mobile phone)—no clinic visit will be required.
- a. Participants will be given the option to come to the VA to complete the questionnaire if desired
 - b. If assessment is not done within a week, researchers will contact the participant to encourage participation and ensure that no adverse events had occurred
 - i. If patients cannot be reached, researchers will attempt to contact them three additional times (one day later, three days later, and one week later). If they cannot be contacted by the third attempt, they will be considered lost to follow-up and will not be contacted again.
16. After the participant completes the study, a retrospective chart review will be conducted to obtain viral load measurements (minimum of 2) from the participant during the time period beginning 1 month prior to their entry into the study and up to 8 months after their entry into the study (6 months after beginning the intervention sessions).

Protocol deviation in case of COVID-19 concerns:

If the providers within the ID clinic or the VA as a whole determines that attending study visits puts participants’ health at risk due to the spread of COVID-19, then TRAC participants will be given the option

to complete all study tasks remotely. The following changes to the protocol will occur until the risk of attending study visits is determined to have been returned to an acceptable level:

1. All screening will occur via phone (study screener and cell phone screener)
2. If participants are eligible and interested in the study, the consent form and HIPAA release will be sent via mail to participants. The interventionist will call participants to review both documents and answer any questions. Once they are signed, participants will use a pre-paid envelope to send them back to the VA.
3. Following receipt of the consent and HIPAA forms, participants will be shipped study equipment (breathalyzer and cell phone, if applicable), participant manuals, and ClinCards, and the interventionist will reach out to schedule the initial appointment.

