4. The first visit will be conducted using videoconferencing on the participants' mobile phone, and if that is not possible due to phone or data limitations, a traditional phone call will be held.
5. The remaining part of the study will continue as originally scheduled, and participants will not return to the VA for the Week 8 visit. They will use a pre-paid shipping box to send study equipment back to the VA.
6. Once the equipment is received by the study team, participants will receive compensation owed for the final visit.
7. Participants will also complete all study questionnaires remotely using their own phone or computer, with the option to complete paper questionnaires if needed (mailed to participants' homes).
8. All assessments (daily surveys and study questionnaires) will contain questions related to COVID-19 attitudes, COVID-19-related behaviors, and COVID-19 experiences/exposure.

Step 5: Incentive Distribution

Throughout the intervention, the participant will receive money deposited to a ClinCard debit card or mailed to the participant by check on the following schedule. On the rare occurrence that a study visit is delayed, the participant may receive additional compensation equivalent to the monitoring tasks completed, but no more than \$30:

Intervention Group

- After Session 1: \$20 for in-person session, \$30 for questionnaire
- After Session 2: \$20 for phone session, up to \$15 for daily monitoring
- After Session 3: \$20 for phone session, up to \$15 for daily monitoring
- After Session 4: \$20 for phone session, up to \$15 for daily monitoring
- After Session 5: \$20 for phone session, up to \$15 for daily monitoring
- After Session 6: \$20 for phone session, up to \$15 for daily monitoring
- After Session 7: \$20 for phone session, up to \$15 for daily monitoring
- After Session 8: \$20 for phone session, plus up to \$15 for daily monitoring
- After Week 8 visit to the VA: \$40 for questionnaire, plus up to \$15 for daily monitoring
- After Week 12 Booster Session: \$20
- After week 16 questionnaire: \$40
- After week 24 questionnaire: \$40

[figure not shown]
Control Group

- After baseline questionnaire: \$30
- After Session 1: \$20 for in-person session, \$40 for questionnaire
- After Session 2: \$20 for phone session, up to \$15 for daily monitoring
- After Session 3: \$20 for phone session, up to \$15 for daily monitoring
- After Session 4: \$20 for phone session, up to \$15 for daily monitoring

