Participants in the proposed research will benefit primarily by receiving free alcohol reduction counseling, which has potential to not only reduce their alcohol use, but improve their HIV medication adherence and, in turn, their overall health. The self-monitoring aspect will also increase their own awareness of their behaviors and potentially improve their ability to recognize contextual predictors that encourage alcohol use or a lack of medication adherence. Finally, participants will receive financial compensation for their participation. All participants will receive these benefits with minimal effort, as the intervention requires few in-person visits, while the rest can be received via mobile phone.

For all participants, there is the potential risk of anxiety or discomfort when reporting opinions or receiving educational intervention content. The interviews and surveys will address sensitive information or information that may cause embarrassment, such as substance use behaviors and mental health status. Additionally, there is also the risk of loss of confidentiality, as identifying information will be collected in order to monitor participants' data throughout the course of the planned research, as well as to obtain their HIPAA authorization.

There are also inherent risks in using communication technologies for delivering a health intervention. The videoconferencing sessions of the intervention will occur over a HIPAA-compliant secure network, so they will pose no risk. However, any of the activities done using mobile phones, including intervention sessions and self-monitoring, are inherently less secure. Participants and study personnel will receive thorough training on how to secure their mobile phones to prevent any unauthorized access to data, and each phone will have the potential to be remotely wiped in case of theft or loss. The study coordinator will explain this issue carefully and get consent of understanding as part of the study protocol.

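### The COVID-19 remote pathway sets no waitlist hold on shipping equipment, so remote controls could use the breathalyzer unprompted before the week-8 comparison

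*Combined protocol and SAP*

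**What the plan says.** **Clinic pathway, waitlist arm (Step 3b).** Item 6: "At 8 weeks, the patient will come into the clinic to begin the intervention". Item 7 has the participant complete the assessment battery on a laptop. Item 8 then hands over the equipment: "If the participant is in need of a study phone, the VA coordinator will provide this phone, along with the breathalyzer, to the participant". Item 9 is Session 1, which includes orientation to the phone and breathalyzer. Item 10 follows: "The day after the first session, participants will begin self-monitoring their alcohol, medication use, and mental health". The order is battery, equipment, training, monitoring, all at or after week 8.

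**Remote pathway (Protocol deviation in case of COVID-19 concerns).** The opening paragraph covers both arms without distinction: "TRAC participants will be given the option" to do all study tasks remotely while the risk lasts. Item 3 gives the shipping rule: "Following receipt of the consent and HIPAA forms, participants will be shipped study equipment (breathalyzer and cell phone, if applicable), participant manuals". The same sentence adds that the interventionist will get in touch to arrange the initial appointment. Item 5 keeps the rest of the study on its original schedule and says "participants will not return to the VA for the Week 8 visit". The section mentions neither randomisation nor the waitlist.

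**Role of self-monitoring.** Section 6 lists it as a benefit of taking part: "The self-monitoring aspect will also increase their own awareness of their behaviors". The intervention description in Section 4 says the breathalyzer's app shows users their current and past readings.

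**Analysis.** The SAP compares the arms over the 8-week intervention period (Kruskal–Wallis, general linear model, Cohen's d). For longer-term effects it pools both arms, since by then everyone has had TRAC.

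**The concern.** The clinic pathway keeps the breathalyzer away from controls until their 8-week battery is done. The remote pathway replaces that timing with a single trigger, the return of signed forms, and no other item in the section restores the hold for Group 2.

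A coordinator applying item 3 as written would send a control a breathalyzer, a manual and, where needed, a phone about eight weeks before the clinic pathway would. The app gives feedback without any study prompt. The plan regards monitoring one's own drinking as part of what makes TRAC work, so controls who used the device on their own might drink less before week 8.

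The stake is the week-8 effect size. It is the only randomised estimate against an untreated group, and the SAP offers it as preliminary evidence of efficacy. Controls enrolled through the clinic and through the remote pathway would also differ in exposure, according to when they joined.

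**Working it through.** The point is mainly textual, so the two pathways are set side by side for a waitlist participant.

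| Step | Clinic pathway (Steps 2 and 3b) | Remote pathway (COVID-19 items) |
|---|---|---|
| Manual | Listed at enrollment for Group 1 only (Step 2, item 5a) | Shipped after forms are received, no arm named (item 3) |
| Breathalyzer and phone | Week 8, after the battery (3b, items 6–8) | Shipped after forms are received, no arm or week named (item 3) |
| Scheduling of Session 1 | Week 7 contact (3b, item 4) | Mentioned with shipping, no week named (item 3) |
| Training, prompts, surveys | At Session 1 and from the day after (3b, items 9–10) | No change stated |
| Return of equipment | Week 16 (3b, item 13) | Attached to the Week 8 visit (item 5) |

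The first two rows conflict. Item 5's clause about the original schedule does not settle them, because it governs what remains after the shipping and first-visit items.

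**Is any control monitoring planned before week 8?** The payment schedule answers this. Each arm has nine sessions at $20, eight weeks of monitoring at up to $15, and questionnaires at $30, $40, $40 and $40:

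9 × 20 + 8 × 15 + 30 + 3 × 40 = 180 + 120 + 30 + 120 = 450.

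This reproduces the stated total of $450. In the control schedule all eight monitoring payments come after Session 1. No monitoring by controls is planned or paid in weeks 0 to 8, so the possible exposure is unprompted use only.

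**Illustration of size.** The documents give no effect size, no share of remote controls and no share of the effect due to monitoring. Let d be the true standardised difference, f the share of controls who use the device early, and s the share of the TRAC effect that such use reproduces. Then

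observed d = d × (1 − f × s).

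Assume 25 per arm (N = 50; the allocation ratio is not stated) and a two-sided 5% level (sidedness is not stated). Approximate power is Φ(observed d × √(25/2) − 1.96).

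| f | s | observed d (power), true d = 0.5 | observed d (power), true d = 0.8 |
|---|---|---|---|
| 0 | – | 0.50 (0.42) | 0.80 (0.81) |
| 0.25 | 0.25 | 0.47 (0.38) | 0.75 (0.76) |
| 0.5 | 0.25 | 0.44 (0.34) | 0.70 (0.70) |
| 0.5 | 0.5 | 0.375 (0.26) | 0.60 (0.56) |
| 1 | 0.5 | 0.25 (0.14) | 0.40 (0.29) |

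For example, with f = s = 0.5 and d = 0.5: 0.5 × (1 − 0.25) = 0.375. Untrained, unpaid use probably reproduces less of the effect than full TRAC monitoring does, so the lower values of s are the more plausible ones.

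**The case against.** **Item 3 can be read more gently.** It sets shipment after receipt of forms, not at once, and the same sentence ties it to arranging the initial appointment, which for the waitlist arm happens at week 7. The section lists changes only and does not suspend randomisation or the Step 3b timeline. Staff could ship to controls near week 8 and comply. This stands as a permitted reading, but nothing requires it. The participant-timeline flowchart mentioned under Study Schedule could not be read for this review.

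**Holding a device is not receiving TRAC monitoring.** A reader might infer that controls would get the monitoring component itself in weeks 0 to 8. The documents do not support that: training, the two daily texts, surveys, payment and counselor review all begin with or after Session 1. This objection stands and limits the point to unprompted use.

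**Item 5 loses nothing.** A reader might infer that cancelling the Week 8 visit removes the controls' 8-week battery and first session. Items 4 and 7 provide for both remotely, and the text around item 5 concerns sending equipment back. It is a labelling slip that uses Group 1's week.

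**Step 2, item 6f does little alone.** It is not limited by arm: "Ask the participant to view the instructions for downloading the BACTrack app in the Participant Manual and ask them to download it". But an app without a breathalyzer takes no readings. It matters only once the device has arrived early.

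**The bias is small beside the noise.** At d = 0.5 with 25 per arm the standard error is √(2/25 + 0.5²/(2 × 50)) ≈ 0.29, larger than every attenuation shown for that d (0.03 to 0.25). The SAP also disclaims power. That is correct, but sampling noise does not excuse an avoidable systematic error in an estimate meant to inform later work.

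**Conclusion.** The conflict is real: COVID-19 item 3 and Step 3b items 6 to 8 give different times for equipping waitlist participants, and no text reconciles them. Followed literally, item 3 lets controls who take the remote option hold a working breathalyzer before their 8-week battery.

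The consequence is conditional. If some of them use it unprompted, and if that reduces drinking, the week-8 difference is biased toward zero. It would be too strong to say that the effect size is biased, or that every control is affected. The pathway is optional and temporary, use is only possible, and early shipment is not the sole reading.

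The size cannot be derived. The range in the table (0.47 to 0.25 for a true 0.5; 0.75 to 0.40 for a true 0.8) rests entirely on assumed values of d, f and s. Confidence is high in the textual conflict and low in any figure for the bias.

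**What to change.** 1. **Split item 3 by arm.** After the forms arrive and allocation is checked, ship equipment and manual to Group 1. For Group 2, time shipment to the week-7 scheduling contact, with a written instruction not to use the equipment until the remote 8-week battery is submitted and Session 1 begins. This has to be an instruction, since the documents describe no way to lock or activate a breathalyzer remotely.
2. **Relabel the visit in item 5** as the final VA visit: Week 8 for Group 1, Week 16 for Group 2.
3. **Log the equipment delivery date** for every participant.
4. **If any control was equipped before the 8-week battery**, add a sensitivity analysis of the week-8 comparison that restricts both arms to the same enrollment period, outside the remote pathway. Dropping only the early-equipped controls would remove pandemic-period participants from one arm and keep them in the other, which breaks the randomised comparison and confounds arm with calendar time.

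The cost is a short amendment and one extra scheduling step for remote waitlist participants. Shipments are delayed, not added. The sensitivity analysis, if needed, uses fewer participants and will be less precise.
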